## GLOSSARY OF TERMS AND ABBREVIATIONS

AE	Adverse Event
AFP	Alpha-fetoprotein
AR	Adverse Reaction
AUC	Area under the Curve
BEP	Bleomycin, Etoposide, Cisplatin
CI	Chief Investigator
CIOMS	Council for International Organizations of Medical Sciences
CR	Complete Response
CRF	Case Report Form
CT	Computed Tomography
CTCAE	Common Terminology Criteria for Adverse Events
ECOG	Eastern Cooperative Oncology Group
EDTA	Ethylenediaminetetraacetic acid
EU	European Union
FAS	Full Analysis Set
FDG	Fluorodeoxyglucose
FSH	Follicle-stimulating hormone
GCP	Good Clinical Practice
GCSF	Granulocyte Colony-Stimulating Factor
GFR	Glomerular Filtration Rate
hCG	Human Chorionic Gonadotropin
ICH	International Council for Harmonization
IEC	Independent Ethics Committee
IGCCCG	International Germ Cell Cancer Collaborative Group
IMP	Investigational medicinal product
JRO	Joint Research Office
LDH	Lactate Dehydrogenase
LFTs	Liver Function Tests
LH	Luteinizing hormone
MDT	Multidisciplinary Team Meeting
ml/min	millilitre/minute
MRC	Medical Research Council
MREC	Multi Research Ethics Committee
NHS	National Health Service
OCTG	Orchid Clinical Trials Group
PD	Progressive Disease
PET	Positron Emission Tomography
PFS	Progression Free Survival
PI	Principal Investigator
PR	Partial Response
PS	Performance Status
SAE	Serious Adverse Event
SAR	Serious Adverse Reaction
SD	Stable Disease
SOP	Standard operating procedure
SPD	Sum of Product of the Diameters
SS	Safety Set
SUSAR	Suspected Unexpected Serious Adverse Reaction
SUV	Standard Uptake Value
U&Es	Urea and Electrolytes
WBC	White Blood Count

## Protocol Synopsis

Title	A multi-centre phase II study using carboplatin AUC-10 for metastatic seminoma with IGCCCG good prognosis disease – therapy directed by initial metabolic response on PET-CT.
Short Title	Car-PET
Protocol Version Number and Date	Version 8.0 (31 Aug 2017)
Methodology	This is a single arm phase II trial to assess the safety, efficacy and toxicity of carboplatin AUC-10 in metastatic seminoma. Patients will be recruited from 2 sites.
Study duration	48 months for recruitment. 2 years for follow up.
Study centres	Multisite.
Objectives	
 
• To assess the safety, efficacy and toxicity of carboplatin AUC-10 in metastatic seminoma in a multi-centre setting.
 
• To see if the number of patients requiring 4 cycles can be reduced by the use of FDG PET-CT in the assessment of metabolic response.
 

Phase of Trial	II
Number of patients	Up to 50 patients will be recruited into the study over four years (assuming 5 patients may drop out for reasons other than disease progression). 45 evaluable patients will be necessary to establish activity of Carboplatin AUC10 in this setting.
Inclusion criteria	
 
1. Metastatic seminoma-IGCCCG good prognosis.
 
2. Glomerular filtration rate of over 25 ml/min (creatinine clearance should preferably be assessed using an EDTA clearance).
 
3. ECOG performance status 0-3.
 
4. Normal Alpha-fetoprotein (All levels of Human chorionic gonadotropin and lactate dehydrogenase are acceptable).
 
5. Males aged greater than 18 and less than 75 years.
 
6. Able to give written informed consent prior to study entry.
 
7. Patients must be sterile or agree to use adequate contraception during the period of therapy.
 

Exclusion criteria	
 
1. Metastatic seminoma with any non-pulmonary visceral metastases.
 
2. Raised Alpha-fetoprotein.
 
3. Any previous chemotherapy or radiotherapy.
 
4. Currently enrolled in any other investigational drug study.
 
5. Other malignancy except basal cell.
 

Statistical Methodology and Analysis	
The primary efficacy endpoint is the Progression Free Survival (PFS) rate at 2 years from completion of treatment. Patients who do not complete 2 years follow-up for reasons other than death will be censored at the last date of follow-up. The PFS rate will be determined for the Carboplatin AUC-10, along with a 95% confidence interval, and the Kaplan-Meier curves will be plotted. The trial result will be considered positive if the PFS rate for patients on Carboplatin AUC-10 demonstrates an increase in survival of 15% or more when compared to PFS rates of standard chemo i.e. if there are at least 39 PFS patients out of first 45 patients at 2 years.
 
Subgroup analyses of the PFS rate will be performed in terms of patients with complete or partial response at 2 years. The analysis of safety will include all patients who received at least one cycle of treatment. Safety and tolerability of Carboplatin AUC-10 will be determined by an evaluation of changes in laboratory parameters, vital signs, the incidence and severity of Adverse Events and of toxicities according to the CTCAE classification (version 4.03). The proportion of patients at each toxicity grade (0 to 4) of any type (including vomiting, nausea and diarrhoea) will be summarised. Safety analysis will be performed based on safety data set.
 
Metabolic response rate will be assessed as described in section 5.3.3 of the protocol.

---	--

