## 11.2 Statistical considerations

### 11.2.1 Sample Size

The primary objective is to gain a preliminary indication on whether carboplatin AUC-10 is worthwhile considering in a phase III study, using the progression free survival (PFS) rate as a criterion. A'Hern's single-stage procedure is used to estimate the number of patients required [8].

The primary outcome is the percentage of patients progression-free at 2-years. Therefore, all patients must have at least 2-years follow-up (unless they have died or their disease has progressed). An MRC study [1] showed that PFS rate at 3 years in standard chemotherapy, BEP, is 81%. It is also known that PFS rate at 2-years and 3-years are the same [2]. Carboplatin AUC-10 should not therefore have a 2-year PFS rate of 75% or less, and it would only be worth considering in a phase III study if the true rate were 90% or more. This information is used in A'Hern's single stage design to yield a sample size of 45 patients, with 80% power and one-sided test of significance at the 5% level. Here the statistical assumption of this design is that there is 80% chance of concluding that Carboplatin AUC-10 is effective if the true response rate is 90% or more, but only a 5%

chance of concluding it is effective if the response rate is 75% or less. To allow for a 10% drop-out rate the intention is to recruit 50 patients.

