### **11.5 Primary endpoint analysis**

The primary efficacy endpoint is Progression Free Survival (PFS) rate at 2 years. Patients who do not complete 2 years follow-up for reasons other than death will be censored at the last date of follow-up. The PFS rate will be determined for the Carboplatin AUC-10, along with a 95% confidence interval, and the Kaplan-Meier curves will be plotted. The study result will be considered positive if the PFS rate for patients on Carboplatin AUC-10 is consistent with a true difference of 15% or more from standard chemo i.e. if there are at least 39 PFS patients out of the first 45 patients at 2 years.

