1.2 Purpose of the Analyses

These analyses will assess the safety, efficacy and toxicity of carboplatin AUC-10 in metastatic seminoma in a multi-centre setting. The aim is to see if, by using Fluorodeoxyglucose (FDG) PET-CT to assess metabolic response, the number of patients requiring 4 cycles can be reduced.

2 Study Objectives and Endpoints

Primary Objective	Endpoints
2-year PFS rate	PFS rate for carboplatin AUC-10 at 2 years measured from the date of study enrolment to the date of disease progression or death. The study result will be considered positive if the PFS rate for patients on carboplatin AUC-10 is consistent with a true difference of 15% or more from standard chemo i.e. if there are at least 39 PFS patients out of the first 45 patients at 2 years.
Secondary Objectives	Endpoints

Metabolic response rate	Proportion of patients meeting each of the response categories as defined in Appendix 2 of the protocol.
Overall response	Overall response at the end of the treatment
Overall survival	Median overall survival time measured from the date of study enrolment to the date of death.
Toxicity level	Percentage of adverse events (grade 3 or 4 according to CTCAE version 4.03 criteria) in terms of treatment cycle of any type (including vomiting, nausea and diarrhoea).

3 Study Methods

[figure not shown]

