3.4.1.2.2. Overall Survival

Overall survival is defined as the time from date of enrolment to the date of death due to any cause. All deaths will be included, whether they occur on study treatment or following treatment discontinuation. For patients who have not died, OS will be censored at the date of last contact. Methods for handling censoring and for analysis are the same as those described for PFS.

4 Sample Size

The primary objective is to gain a preliminary indication on whether carboplatin AUC-10 is worthwhile considering in a phase III study, using the PFS rate as a criterion. A'Hern's single-stage procedure is used to estimate the number of patients required [3].

The primary outcome is the percentage of patients progression-free at 2-years. Therefore, all patients must have at least 2-years follow-up (unless they have died or their disease has progressed). A Medical Research Council (MRC) study [1] showed that PFS rate at 3 years in standard chemotherapy, bleomycin, etoposide, cisplatin (BEP), is 81%. It is also known that PFS rate at 2-years and 3-years are the same [2]. Carboplatin AUC-10 should not therefore have a 2-year PFS rate of 75% or less, and it would only be worth considering in a phase III study if the true rate were 90% or more. This information is used in A'Hern's single stage design to yield a sample size of 45 patients, with 80% power and one-sided test of significance at the 5% level. Here the statistical assumption of this design is that there is 80% chance of concluding that carboplatin AUC-10 is effective if the true response rate is 90% or more, but only a 5% chance of concluding it is effective if the response rate is 75% or less. To allow for a 10% drop-out rate the intention is to recruit up to 50 patients.

5 General Considerations

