7.2 Primary Efficacy Analysis

7.2.1 PFS

Kaplan-Meier (K-M) methodology will be used to estimate the median PFS. The median PFS and PFS rate for carboplatin AUC-10 at 2-years will be estimated with one-sided 95% CI to be consistent with one-sided test. However, 2-sided 95% CI will also be presented. The study result will be considered positive if the PFS rate for patients on carboplatin AUC-10 is consistent with a true difference of 15% or more from standard chemo i.e. if there are at least 39 PFS patients out of the first 45 patients at 2 years.

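### Reaching 39 of 45 rejects a 2-year PFS rate of 75%; it does not show a 15% gain over standard chemotherapy, which the plan itself puts at 81%

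*Protocol*

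**What the plan says.** The success rule appears four times with the same count but not the same meaning.

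- Protocol Synopsis (Statistical Methodology and Analysis): the result is positive if the PFS rate "demonstrates an increase in survival of 15% or more when compared to PFS rates of standard chemo i.e. if there are at least 39" of the first 45 patients are progression-free at 2 years.
- Protocol 11.5: the PFS rate must be "consistent with a true difference of 15% or more from standard chemo i.e. if there are at least 39 PFS patients" of the first 45.
- SAP section 2 (endpoint table) and SAP 7.2.1: again "consistent with a true difference of 15% or more from standard chemo", with the same count. SAP 7.2.1 adds that the 2-year rate "will be estimated with one-sided 95% CI to be consistent with one-sided test", with a two-sided 95% interval alongside. No interval method is named.

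The count is derived in Protocol 11.2.1 and SAP section 4. The unacceptable rate is 75% or less, and "it would only be worth considering in a phase III study if the true rate were 90% or more". SAP section 4 gives the error rate as "only a 5% chance of concluding it is effective if the response rate is 75% or less". The same sections state the rate on standard treatment: "PFS rate at 3 years in standard chemotherapy, BEP, is 81" per cent. They carry it back to 2 years on the ground that the "PFS rate at 2-years and 3-years are the same". Protocol 1.1 and SAP 1.1 say over 81%. Neither document puts standard chemotherapy at 75%.

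**The concern.** The synopsis joins the claim and the count with *i.e.*, so 39 of 45 is presented as equivalent to having shown a gain of 15% or more over standard chemotherapy. The test behind the count has 75% as its null, and 75% is not the plan's rate for standard treatment. The 15 points are probably the distance from 75% to 90%. That is an inference, because the documents do not say where the figure comes from. Measured from 81%, the plan's own 90% target is a gain of only 9 points, or 11% relative, so even the true rate the trial hopes for would not meet the description in the synopsis.

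This is the trial's only formal success rule. The go/no-go decision is not in doubt; what a positive result may be said to mean is. As worded, 39 of 45 could be reported, in line with the protocol, as a 15% improvement on standard chemotherapy.

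**Working it through.** **Inputs.** n = 45, cut-off 39, null 75%, alternative 90%, one-sided 5%, power 80% (Protocol 11.2.1, SAP section 4; cut-off from Protocol 11.5). Standard rate 81%, taken as equal at 2 and 3 years (Protocol 11.2.1). All calculations assume 2-year status is known for all 45 patients.

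**1. The plan's design.** With X binomial(45, p):

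- P(X ≥ 39 | p = 0.75) = 0.0446
- P(X ≥ 39 | p = 0.90) = 0.8415

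A search over n finds 45 with cut-off 39 to be the smallest design with alpha at most 5% and power at least 80%. The plan's figures reproduce, and 45/(1 − 0.10) = 50 gives the recruitment target.

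**2. What 15% over standard would mean.**

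| Reading | Target rate | × 45 | Smallest observed count |
|---|---|---|---|
| Points | 0.81 + 0.15 = 0.96 | 43.2 | 44 |
| Relative | 0.81 × 1.15 = 0.9315 | 41.9 | 42 |

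The cut-off is 39/45 = 0.8667. That is 0.8667 − 0.81 = 0.057 above standard, or 0.8667/0.81 = 1.07, a 7% relative gain. So 39 falls short of a 15% gain on either reading, even as a bare observed rate.

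The plan's target compares as 0.90 − 0.81 = 0.09 and 0.90/0.81 = 1.11.

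**3. What 39/45 excludes.** Because no interval method is named, four are shown.

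| Method | One-sided 95% lower limit | Two-sided 95% upper limit |
|---|---|---|
| Exact (Clopper-Pearson) | 75.4% | 94.9% |
| Log-log | 75.6% | 93.8% |
| Wilson | 76.2% | 93.7% |
| Wald | 78.3% | 96.6% |

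Every lower limit lies above 75% and below 81%. The data at the cut-off therefore reject 75% and do not reject the plan's standard rate, whichever method is used.

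**4. How often the rule is met with no gain.** P(X ≥ 39 | p = 0.81) = 0.223. A treatment exactly as good as standard would be declared positive about 22% of the time.

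**5. The softer wording.** Whether 39/45 is compatible with 96% depends on the method: the upper limit is below 96% for exact, log-log and Wilson, and above it for Wald. The relative target of 93.2% lies inside all four intervals. So *consistent with* cannot be called numerically false. It is undefined, and it names the wrong comparator.

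**The case against.** The strongest reply is that the strong verb occurs once, in a synopsis, while the sections that direct the analysis (Protocol 11.5, SAP sections 2 and 7.2.1) use the softer phrase. Each statement is followed by the explicit count, which fixes the decision, and Protocol 11.2.1 and SAP section 4 say correctly what the count tests. Protocol 11.2.1 describes the aim as a preliminary indication, Protocol 11.3 calls all analyses exploratory, and the planned confidence intervals would show 81% inside them at the cut-off. On this view the point is a minor clarification.

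Much of this stands. The decision rule is unaffected, and the exploratory framing and the intervals lower the risk of misreporting. But they conflict with the synopsis sentence without correcting it, and the three softer statements still measure the 15% from standard chemotherapy.

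The 15% might also have another origin: 0.75 × 1.15 = 0.8625, and 0.8625 × 45 = 38.8, which rounds up to 39. This fits the cut-off, so the intended meaning is open. It does not help the wording, because it too starts from 75%.

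It is also fair to say that alpha 0.045 and power 84% hold only when 2-year status is known for all 45. If one of the 45 has no 2-year status and cannot count towards 39, power at 90% falls to 73%; with two such patients it is 57%. The replacement text should carry that condition.

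**Conclusion.** The concern holds. The synopsis statement is wrong as written: 39/45 is 5.7 points above the plan's standard rate, its one-sided 95% lower limit (75.4% to 78.3%) does not exclude 81%, and the rule is met 22% of the time at a true rate of 81%. The other three statements have a narrower fault, namely a wrong comparator and an undefined phrase. The sample size, cut-off and go/no-go decision are sound for 75% against 90%.

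The conclusion rests on 81% as the 2-year rate on standard chemotherapy, which is the plan's own statement. If the rate is over 81%, as the background sections say, the gap widens. It also assumes no censoring before 2 years among the 45. The wording should be corrected, since it governs what the trial's only success rule may be taken to show.

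**What to change.** In the Protocol Synopsis, Protocol 11.5, SAP section 2 and SAP 7.2.1, remove the 15% comparison with standard chemotherapy and substitute one common statement, for example:

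> The result is positive if 39 or more of the first 45 patients are progression-free at 2 years. With 2-year status known for all 45, this rejects a true 2-year PFS rate of 75% or less (exact one-sided alpha 0.045; power 84% at a true rate of 90%). It is not a test of superiority over standard chemotherapy (81%).

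This also removes the synopsis's reference to survival where the endpoint is PFS. If the sponsor wants to keep a 15-point figure, it should be stated as the distance from 75% to 90%, provided the sponsor confirms that this was meant.

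The cost is a wording amendment in four places and a less favourable stated claim. Sample size, cut-off, the first-45 denominator and data collection do not change.

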## **1.0     Introduction**

### **1.1     *Background***

Metastatic seminoma is a relatively infrequent disease entity. The conventional treatment for it, namely cisplatin and etoposide with or without bleomycin, has a progression free survival rate at 3 years of over 81% compared to 71% treated with Carboplatin AUC 7 [1]. The overall survival however, is identical due to the effectiveness of second line salvage chemotherapy. The conventional treatment is toxic, usually requires an inpatient stay with administration over 3 days and can cause significant nausea, malaise, alopecia, risk of renal damage, hypertension and high tone hearing loss. It is possible to give this treatment on an outpatient basis however, this can be inconvenient as the patient has to attend for prolonged visits to a chemotherapy day ward for a minimum of 3 consecutive days for each cycle of treatment. Single agent carboplatin does not appear to have long term renal and hearing problems. There is no alopecia. Nausea and malaise are much less common and the treatment can be given as a day case with only one visit to hospital for one hour per cycle they receive.

### **1.2     *Investigational agent***

A variety of observations have led to the impression that seminomas are inherently more chemo-sensitive than non-seminomatous germ cell tumours. Several studies have addressed the use of single agent carboplatin in metastatic seminoma. Studies have generally concluded that although progression free survival is inferior to that seen with cisplatin based therapy, as a large number of relapsing patients could be salvaged, the overall survival was unchanged and indeed toxicity was substantially reduced [1, 2]. There is clear evidence for a dose response curve to platinum drugs in germ cell tumours; although certainly in metastatic non-seminomatous tumours there is little evidence to support intensification from AUC-5 to AUC-8 [3, 4]. In other tumour types notably epithelial carcinoma of the ovary, higher doses of carboplatin (AUC-12) have proved feasible although the increasing dose intensity has been smaller than anticipated because of delays in retreating patients due to the prolonged myelosuppression [5].

### **1.3 Clinical data to date**

The Orchid Clinical Trials Group recently completed a study in metastatic seminoma using carboplatin AUC-10. Twenty patients received this dose of carboplatin for metastatic seminoma, with a median follow up of 29.4 months. Following the closure of the study a further 20 patients have received carboplatin AUC-10. In total 40 patients have been treated. There have been 2 relapses to date (5%), compared to the 18% relapse seen within the first 2 years of treatment of 28 patients who received AUC 7 or less with a median follow up of 135 months.

The relapsed patients were successfully salvaged using conventional chemotherapy. As nearly all relapses occur within 2 years of therapy, a 2 year progression-free survival is an appropriate endpoint for this phase II study.

In this most recent study, the protocol stipulated that all patients who were not in complete remission by day 21 of the first cycle would receive 4 rather than 3 cycles. This led to all those who essentially had greater than 2B disease requiring 4 cycles. This was probably unnecessary as most patients achieved a CR eventually – it just took time for the masses to shrink.

It is hoped that by substituting conventional CT for PET CT a greater proportion of patients will achieve a complete metabolic response and therefore the 4th cycle may be avoided in more patients. This will allow shortening of the treatment and reduction in the use of blood products as most of the blood transfusions required occur during the 4th cycle of carboplatin.

### **2.0 Study aims and objectives**

- To assess the safety, efficacy and toxicity of carboplatin AUC-10 in metastatic seminoma in a multi-centre setting.
- To see if, by using FDG PET-CT to assess metabolic response, the number of patients requiring 4 cycles can be reduced.

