## **2.1 End points**

- **Primary**  
2-year progression free survival
- **Secondary**  
Metabolic response rate  
Overall survival  
Toxicity level (CTCAE version 4.03)

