## **3.0 Investigational plan**

### **3.1 Overall design**

This is a single arm phase II study to assess the safety, efficacy and toxicity of carboplatin AUC-10 in metastatic seminoma. Patients will be recruited from two sites.

Prior to the commencement of treatment, the patient should have a baseline PET-CT scan and a contrast enhanced CT scan performed within 28 days of study entry. Patients will be treated with carboplatin AUC-10 every 3 weeks (3 weeks=1 cycle) and on day 17-21 of the first cycle a repeat PET-CT scan will be performed. All PET-CT scans will be reviewed centrally and these results will determine how many further treatment cycles the patients will undergo. If the patient has a complete metabolic response [refer to Appendix 3], a further 2 cycles of carboplatin will be given, leading to a total of 3, and if the patient has not had a complete metabolic response but is responding, a further 3 cycles of carboplatin will be given [Refer to section 5.3.3 and page 20 (the table) for the timelines for the scans. Please refer to appendix 8 for the imaging protocol].

If no response is seen, then the patient will be taken off study and will receive conventional therapy using a cisplatin-based combination.

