### 5.3.3 Central review of PET-CT scans

There are currently no well validated metabolic response criteria for PET-CT in seminoma. Hence, we will use the criteria for assessment of response developed for the evaluation of lymphoma [6].

A Complete Response will be defined as **complete resolution** of all previously seen sites of nodal and metastatic disease. If residual sites of metastatic disease persist then the PET-CT will be used to evaluate metabolic activity.

Metabolic Complete Remission will be defined as the level of FDG uptake within the lesion that is no greater than normal mediastinal uptake these patients will receive 3 cycles in total. Lesions with uptake greater than the mediastinum will be viewed as non-complete

responders. The PET data will be viewed on standardised SUV (standardised uptake value) setting of between 0 and 5.0 and a visual comparison will be made to assess the degree of uptake within abnormal tissue [7]. These criteria will have a high probability of distinguishing true complete responders from partial responders. Contrast enhanced CTs will be evaluated via the standard response criteria (Appendix 4).

All PET-CT scans will be centrally reviewed at University College London Hospital. The results from the report will be used to determine the number of further treatment cycle's patients will require, following cycle 1. Copies of locally reported scans (where relevant) should be sent to the central reviewer via the secure NHS Image Exchange Portal system (IEP) for review by the central reviewer (please refer to appendix 7). Sending images via IEP will not apply to sites where patients are scanned at UCLH, however, sites must ensure that the proforma is completed and sent to remind the central reviewer. In addition to sending images via the secure IEP system, sites must email a copy of the Proforma Request form (see Appendix 5 and 6) that is appropriate to each site) to the central reviewer to indicate that an image has been sent via IEP.

The central reviewer will review the image and return the generated report within the appropriate timelines as stated in the table below (see Appendix 7);

All scans for central review to be sent to;

[name]

Consultant in Nuclear Medicine

Institute of Nuclear Medicine, T5

University College Hospital

[name],

[name]

[contact]

Proforma Request form to be emailed to: [[contact]](mailto:[contact]) and  
[[contact]](mailto:[contact])

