7.3 Secondary Efficacy Analysis

7.3.1 Metabolic Response Rate

The number and percentage of subjects falling into each response category defined in Appendix 2 of the protocol i.e. the categories of: CR, PR marker positive, PR marker negative, stable disease, and progressive disease after one cycle will be descriptively tabulated.

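### The aim of reducing the number of patients needing 4 cycles has no reference or analysis, and SAP 7.3.1 does not identify the patients whose cycle number PET-CT changed

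*Protocol*

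**What the plan says.** Protocol 2.0 has two objectives. The second is "To see if, by using FDG PET-CT to assess metabolic response, the number of patients requiring 4 cycles can be reduced". SAP 1.2 and SAP 3.4.1.1.2.1 repeat it.

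Protocol 1.3 gives the background. In the earlier AUC-10 study, "all patients who were not in complete remission by day 21 of the first cycle would receive 4 rather than 3 cycles". The consequence is described in words only: "This led to all those who essentially had greater than 2B disease requiring 4 cycles". No count or proportion given 4 cycles is stated.

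The design is single-arm (Protocol 3.1). The endpoint nearest to this aim is "Metabolic response rate" (Protocol 2.1). No endpoint in Protocol 2.1, Protocol 11.1 or SAP 2 concerns cycles given or fourth cycles avoided.

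Protocol 5.3.3 reads the scan in two steps. Complete resolution of all known sites comes first, and then: "If residual sites of metastatic disease persist then the PET-CT will be used to evaluate metabolic activity". Residual lesions with uptake no higher than mediastinum count as metabolic complete remission, and those patients receive 3 cycles in total.

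SAP 7.3.1 is the planned analysis. It cites Appendix 2, lists CR, marker-positive PR, marker-negative PR and stable disease, and ends with "progressive disease after one cycle will be descriptively tabulated". The compliance summaries in SAP 6.5 do not include the number of cycles received.

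**The concern.** A reduction has to be measured against something. Counting the patients who received 4 cycles in this trial says nothing about how many would have received 4 without PET-CT. The only implied reference is the earlier study. There the fourth cycle followed disease bulk, so a comparison across studies would shift with the stage mix.

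The risk is misreading. A high complete response rate after cycle 1 may partly reflect low-bulk patients who would have had 3 cycles under the earlier rule too. It could then be credited to PET-CT. The patients who bear on the aim are those with a residual mass who received 3 cycles because the scan was metabolically clear. Their number and their progression-free survival are the informative results, and neither is planned. The PFS subgroups in Protocol 11.6 are defined by response at 2 years, not at day 17-21.

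**Working it through.** **The plan's own figure.** The documents state no figure for the 4-cycle aim. The only design calculation is for the primary endpoint (Protocol 11.2.1 and 11.5), and it reproduces. With at least 39 successes of 45 required, the exact binomial gives P(X ≥ 39) = 0.0446 at a true rate of 75% and 0.841 at 90%. The smallest n meeting 5% and 80% is 45, and 45 / (1 − 0.10) = 50. Nothing below changes this.

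**Groups formed by the two rules.** The earlier rule is in Protocol 1.3 and the current reading in Protocol 5.3.3, taken in its two-step order.

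| Day 17-21 finding | Earlier CT rule | PET-CT rule |
|---|---|---|
| A: all sites resolved | 3 cycles | 3 cycles |
| B: residual mass, complete metabolic response | 4 cycles | 3 cycles |
| C: residual mass, metabolically active, responding | 4 cycles | 4 cycles |
| D: no response | not compared | off study |

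Group B is where PET-CT avoids a fourth cycle. The estimate is B / N.

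**Whether SAP 7.3.1 gives B.** There are two readings.

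- Appendix 2, as cited: its CR allows a mass of any size if PET negative, so CR = A + B. As an illustration only, if 30 of 45 are in CR, then B = 30 − 25 = 5 if 25 had resolved, or 30 − 5 = 25 if 5 had resolved. The CR count is 30 in both cases.
- Appendix 3-type categories, as listed: CR requires no radiological disease and normal markers. A residual mass with normal markers is marker-negative PR whatever its PET status. If 30 of 45 were in that category, B could lie anywhere from 0 to 30 on those numbers alone.

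B is identified on neither reading.

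**Precision if B is reported.** The documents give no value for B, so a range is assumed. Exact (Clopper-Pearson) 95% CIs with N = 45 are:

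| B | Proportion | 95% CI |
|---|---|---|
| 4 | 8.9% | 2.5-21.2% |
| 9 | 20.0% | 9.6-34.6% |
| 15 | 33.3% | 20.0-49.0% |
| 18 | 40.0% | 25.7-55.7% |
| 27 | 60.0% | 44.3-74.3% |

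Half-widths run from (21.2 − 2.5) / 2 ≈ 9 points to (74.3 − 44.3) / 2 = 15 points. PFS within B would be imprecise: 14 of 15 progression-free has an exact 95% CI of 68-99.8%.

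**The alternative, a historical comparison.** Protocol 1.3 reports 20 patients in the completed study and then "In total 40 patients have been treated"; it does not say which cycle rule the later 20 followed. Assume a historical 4-cycle share of 40% to 80%, 45 new patients, a two-sided 5% level and 80% power. The detectable drop is then about 31 to 37 points against 20 historical patients, or about 27 to 30 points against 40. Differences in stage mix would remain.

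**The case against.** The strongest case against has four parts.

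- **The aim is secondary and all analyses are declared descriptive (Protocol 11.3).** This is true and limits the seriousness, but a descriptive aim still needs a defined quantity.
- **Usable data are collected.** Number of cycles and metabolic response are source-verified for every patient (Protocol 10.2), stage is summarised at baseline (SAP 6.2) and total exposure is summarised (SAP 8.1). A stage-by-cycles description could be made. This stands, and a reader who concluded that the trial cannot address the aim at all would go too far. The gap is that no such analysis or reference is planned.
- **The day 17-21 scan does not settle what the earlier rule would have given.** A reader might infer that it does. The documents do not support that. The CT component is low dose (Protocol 5.3.3). CR in Appendix 3 and in SAP 7.3.2, which uses the previous study's criteria, also needs normal markers. Day 17-21 markers are listed in Protocol 5.3.2 but not marked in that column of 5.4, and footnote 3 of 5.4 allows the scan up to a week after day 21. A resolved patient with raised markers might have had 4 cycles before.
- **PET-CT might not only move patients from 4 cycles to 3.** The two-step order in 5.3.3 suggests that it does. Under Appendix 2, however, avid disease must become PET negative for CR, so a normal-sized but still avid node could move a patient from 3 to 4. Section 3.1 adds to the uncertainty by referring to Appendix 3, a CT-based definition, for complete metabolic response. If movement is only downward, any non-zero B is a reduction by construction, so the estimate sizes the effect and does not test it.

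**Conclusion.** The point holds. A stated objective is comparative, and the plan gives it no reference, estimate or analysis. SAP 7.3.1 does not isolate the patients whose cycle number PET-CT changed, whichever response definition is applied.

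A reader might infer that the CR category certainly merges resolved disease with PET-negative masses. That holds only under Appendix 2. The categories listed in SAP 7.3.1 point to Appendix 3, where the pooling falls in marker-negative PR instead.

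The effect on the trial's conclusions cannot be sized from the documents, because they give no share for group B. The 5-versus-25 and 15 of 45 figures are illustrations. What can be said is that, with N = 45, B / N would carry a 95% CI half-width of about 9 to 15 points over the assumed range. This rests on treating the anatomical read as a proxy for the earlier rule, which is approximate. The change should be made before database lock. It does not affect the primary endpoint.

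**What to change.** 1. Reconcile SAP 7.3.1, which cites Appendix 2 but lists marker categories of the Appendix 3 type. Reconcile the complete metabolic response threshold too: 5.3.3 uses mediastinum, while Appendix 4 treats scores 1-3, up to liver uptake, as negative. The size of group B depends on both.
2. From the day 17-21 central read, cross-tabulate anatomical complete resolution (yes/no, with tumour-marker status where available) against complete metabolic response (yes/no). Tabulate cycles received.
3. Report descriptively, with an exact 95% CI, the proportion with residual disease on CT but complete metabolic response. Also report any patients reclassified in the other direction, and 2-year PFS in the reclassified group with a note that it will be imprecise. A paired test adds little if movement is essentially one way.
4. State that the earlier-rule classification is approximate, because the CT is low dose and marker timing differs between 5.3.2 and 5.4.

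The cost is one cross-tabulation, one table of cycles and a short SAP amendment, with no new scan, reader or patient. The documents do not show that anatomical resolution is recorded as its own item, so it may have to be extracted from the central reports. Protocol 11.3 leaves further analysis detail to a SAP finalised before database lock, so the change fits the existing process. The sample size and the 39 of 45 rule stay as they are.
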